#### 2. Baseline 1:

- a. Any previously completed WTAR may be substituted for the WTAR for the baseline 1 visit of this study.
- b. Any other component of the baseline 1 visit may be taken instead from an equivalent item previously carried out as long as it is completed within one month of the baseline LP. Although we will try to carry out these assessments in an order and configuration that is consistent across participants, this will not be an absolute requirement; for example, if

PTSD/TBI Glymphatic Protocol Version 3	VA Puget Sound IRB Protocol Template Version: 2/2015	Page 30 of 45
Revised 11/02/2018		

a participant has completed the WTAR two years ago and the ACT and SDMT one week ago, we will only include the CVLT, dot counting test, emotional Stroop test, and PVT for the baseline 1 neurocognitive testing, as the repeated-measure effects from repeating the ACT and SDMT so close together would be more of a concern than the variability in administration context.

- 3. Baseline 2: Any LP completed in the two weeks prior to scheduled randomization date and with sufficient CSF sample collected for our primary outcome measures will be allowed to substitute for the baseline LP. Any previous genetic testing from the prior 10 years may be substituted for equivalent genetic testing in this study.
- 4. Prazosin or placebo titration and maintenance: If a participant is concurrently enrolled in MIRECC prazosin vs. placebo study with overlapping inclusion/exclusion criteria the dosing schedule and data collected from stable dose study treatment period of the **other** study will be used (instead of the schedule for this study), if the following conditions are met:
  - a. The target dose per day of study drug is within 25% of the target dose per day in our study
  - b. The procedures performed at end of study visits 1 and 2, including the associated ambulatory monitoring, will be completed after the participant completes the study treatment period of the concurrent study. We will attempt to coordinate study schedules so there is a mid-point visit that matches when our Stable Dose week 4 visit would be scheduled.
- 5. End of study assessments: substitutions will be allowed as with the baseline assessments, described above.

Any non LP visit-related adverse events will be reported to the IRB for both studies, and it will be noted that the participant is in both studies simultaneously.

Schedule of Study Visitsa:

	Screen	At home, prior to baseline visits	Baseline part 1	Baseline part 2	Standard titration/ follow up visits	Optional titration visits c	Stable dose, Week 1	Stable-dose, Week 4	At home, prior to end of study visits	End of study visits part 1	End of study visits part 2
Visit Number	1		2	3	4-8	1	9	10		11	12
Study Week		-1	0	0	1-5	·	6	9	9-10	10	10
Obtain Consent	X						1937				
Medical and Psychiatric History	X					- '		V September			
Physical exam, Neurological exam	X										2. 注 4. 作。
Urine pregnancy test (women of childbearing potential)	X			Х		(- -	9				X
Screening labs	X		X b			2				Xb	
EKG (if clinically indicated)	X				À ş	5					
Demographic Information, Military History, Combat Experiences Scale	X	,	. ?								
SCID/MINI	X						200			MARTI	Note 119
Quantification of Blast Exposure	X				,						
CAPS	X		X			ę.	100			X	Section 1
TLEQ	X					ş	建筑 建				

PTSD/TBI Glymphatic Protocol Version 3	VA Puget Sound IRB Protocol Template Version: 2/2015	Page 31 of 45
Revised 11/02/2018	,	

	Screen	At home, prior to baseline visits	Baseline part 1	Baseline part 2	Standard titration/ follow up visits	Optional titration visits	Stable dose, Week 1	Stable-dose, Week 4	At home, prior to end of study visits	End of study visits part 1	End of study visits part 2
STOP-BANG Sleep Apnea Screening	X				1						
MoCA	X		X		l l					X	
WTAR			X								
ACT			X							X	
SDMT			X			in its Y		distance in		X	
CVLT			X				11.4		100	X	
Dot Counting Test			X					3 A A		X	
Emotional Stroop Test			X							X	
PVT			X			Kaliffe Kana				X	
PHQ-9			X				X		1200	X	
GAD-7			Х			Million &	X			X	
PSQI			Х		Xg	Xg	X	Xg		X	16-32
VR-12			X				X			X	
DVPRS			X				X			X	A SUV. COM
AUDIT-C			X				X			X	
QCC			Х				Xd			Xd	Sala Lin
CSN			Х				X			X	
PCL			X			had to the	X			X	and the same of th
NSI			X				Х	7.3		X	Marie
Vital Signs	X		X	X	X	X	X	X	17.81	X	X
Review Concurrent Medications			X	X	X	X	X	X		X	X
Review Adverse Events			Х	Х	Х	X	X	X		X	X
Dispense/collect study drug				X	X	X	X	X			X
Wear Actiwatch, Complete Sleep Diary		Х				Page and	Mesenga ha		X	200	
Wear blood pressure/heart rate monitor		X				81 - 1 - 2		1 Harris	X		
Lumbar Puncture				Xc							X
Blood collection for biomarkers/DNA				Xc			1 1 1 1 1 1 1 1 1 1 1 1 1 1 1 1 1 1 1		THE WAY	The second section is	Xf
Estimated Time of Visit (hrs.)	4.5- 6.5		2.5	3	.5	.5	1.5	.5	.5	3	3

<sup>a This schedule may be revised if procedures have been done for a different study within a certain period of time or if participating in two studies simultaneously. Participants will be informed if their existing data can be reused.

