Study Treatment Period: Once the participant has reached his/her highest tolerated dose, he/she will enter the Study Treatment Period. The participant will maintain this dose for a minimum of 5 weeks. A clinic visit will take place at one and four weeks after stable dose is achieved to assess for adverse events. Concomitant medications and health status will be updated. Study drug adherence will be tracked by pill counts.

At the 4 week stable dose visit, we will place the ambulatory blood pressure monitoring equipment, and the participant will be sent home with the Actiwatch and sleep diaries and told to wear them as before.

After 5 weeks at stable dose, participants will undergo cognitive/behavioral testing and sample collection visits just as in baseline visits 1 and 2 (with the exception that blood will not be collected). Ambulatory heart rate measurements will be collected during and following the end of study 1 visit, again as during the baseline period.

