However, ambulatory monitoring will not be done any more than two weeks past baseline LP nor once prazosin has been started, and end of study measures will not be completed any more than two weeks past baseline LP nor once prazosin has been stopped. If necessary, an additional period of up to two weeks delay after the baseline LP but prior to the initiation of prazosin may be added to accommodate this or other scheduling difficulties in obtaining baseline ambulatory monitoring data, and an additional period of up to two weeks of taking the achieved stable prazosin dose may be added to the end of the study in order to accommodate this or other scheduling difficulties in obtaining end of study ambulatory monitoring data. Overnight blood pressure monitoring will not be performed within the 7 day period immediately prior to an LP, to ensure that this procedure does not change the results of the laboratory results via an impact on sleep.

Although all efforts will be made to complete study visits in person, it may be necessary to obtain assessments by telephone. The following actions will be attempted (as appropriate per visit schedule): 1) adverse events will be assessed, 2) assessments shall be completed by telephone interview with the raters, 3) self-rated measures will be provided to participants, then returned by mail using prepaid envelopes, and 4) dispensing of study drug shall be done by trackable shipment. No-show, missed visits and actions taken will be documented in the study record.

In general, we expect that ambulatory monitoring equipment will be returned by participants in person at subsequent visits. If, however, a schedule change, early termination or other unplanned alteration (e.g., a participant forgets to bring it to a visit as planned), there will be two alternative methods for collecting the equipment: first, a member of the study team may go to the participant's location in the community to receive the item from them, or, second, the item can be mailed back using postage-paid, self-addressed packing.

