#### Potential exceptions to study procedures:

Participants already randomized to prazosin versus placebo prior to approval of the protocol modification instituting an initial, phase I open-label phase will continue to receive prazosin versus placebo in a double-blind fashion without alteration. Similarly, an individual who is participating in the study only via dual-enrollment (where the prazosin versus placebo is being administered as part of another study, and it is only assessments being conducted as a part of this study), will continue to be directly enrolled in the phase II version of the trial. All changes in study procedures will only apply to subjects who have not yet been randomized.

PTSD/TBI Glymphatic Protocol Version 3	VA Puget Sound IRB Protocol Template Version: 2/2015	Page 29 of 45
Revised 11/02/2018	,	

Phase I is designed to run until at least 22 participants have completed the full protocol, and their data has been analyzed. As discussed below in the data analysis section, if at the end of phase I the results are potentially consistent with a clinically significant effect, but do not yet meet statistical significance, we will continue the open label portion until we have 37 subjects who have completed the study (15 subjects beyond the initial 22), which is expected to involve 26 additional subjects screened when allowing for expected screen failure and dropout rates.

Some participants may also be (or have been in) in another study longitudinal study of mTBI that is being conducted by the MIRECC research group. If these participants have also agreed to have samples and data stored in the Behavioral Neurosciences Group (BNG) research repository (MIRB #00891, [name] PI), many screening/study assessments and the baseline sample collection may not need to be repeated (as described below).

The MIRECC research group is also conducting a study of the potential efficacy of prazosin in relieving post-traumatic headaches in Veterans with mTBI. Some of these participants will also be eligible for participation in this study. We wish to allow these participants to be in both studies simultaneously in order to maximize scientific learning and medical advances while minimizing participant burden. It also limits potential bias in the results of this study that might come if participants that qualified for competing local studies were enrolled at lower rates than their prevalence in the local community.

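### Nothing in the protocol fixes whether dual-enrolled phase II participants are still on study drug at the outcome lumbar puncture, so some primary outcomes could be measured off drug

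*Combined protocol and SAP*

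**What the plan says.** All of this is in section 5.4 unless noted.

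- **Dual enrolment.** Under the exceptions to study procedures, these participants enter phase II directly. The other trial gives prazosin or placebo, and "it is only assessments being conducted as a part of this study". Item 4 applies the other trial's dosing schedule "instead of the schedule for this study". Item 4b then places the procedures of end-of-study visits 1 and 2, with their ambulatory monitoring, so that they "will be completed after the participant completes the study treatment period of the concurrent study". It adds that staff will try to arrange a visit matching this study's stable-dose week 4.
- **Limit on late measures.** Under the exceptions to the visit schedule, "end of study measures will not be completed any more than two weeks past baseline LP nor once prazosin has been stopped". The same paragraph allows that "an additional period of up to two weeks of taking the achieved stable prazosin dose may be added to the end of the study" to deal with difficulties in obtaining end-of-study monitoring data. It also states: "Overnight blood pressure monitoring will not be performed within the 7 day period immediately prior to an LP".
- **Main schedule.** Under the Study Treatment Period heading, "At the 4 week stable dose visit, we will place the ambulatory blood pressure monitoring equipment", and "After 5 weeks at stable dose, participants will undergo cognitive/behavioral testing and sample collection visits just as in baseline visits 1 and 2". The visit table marks the row for dispensing or collecting study drug at end-of-study part 2, which is the LP visit.
- **Analysis (section 5.5).** The primary outcomes are CSF total tau, p-tau181 and Aβ42. A mixed model is planned for dropouts and for final assessments made before 10 weeks. LPs taken after dosing has ended are not mentioned.

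**The concern.** The hypothesis is about CSF biomarkers under alpha-1 blockade. For most participants, the schedule implies that drug continues up to the LP. For dual-enrolled participants, item 4b asks for the treatment period to be finished first. It puts even the monitoring after that point, and the drug supply belongs to a different protocol. If dosing ends with that period, the outcome LP in part of the prazosin arm measures partial or complete washout. The interval from last dose to LP would then vary among participants pooled in one model. The likely result is a phase II difference biased toward zero, with nothing recorded or prespecified that would reveal it.

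The plan itself treats exposure timing as relevant: section 5.3 requires three months free of alpha-1 antagonists before baseline, because of possible effects on the biomarkers.

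**Working it through.** **Timing, set side by side**

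1. Main schedule: blood pressure monitoring starts at stable-dose week 4 (study week 9), the end-of-study visits are in week 10, and the drug row is marked at the LP visit. Monitoring therefore begins on drug, and the table is consistent with dosing up to the LP.
2. Item 4b: monitoring and LP both come after the other trial's treatment period.
3. With at least 7 days required between overnight blood pressure monitoring and an LP, a participant monitored only after that period would have the LP at least 7 days after it ended.
4. The optional extension is up to 14 days, so it could cover the 7 days. It is discretionary, and for these participants it works only if the other trial goes on supplying drug.

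**Size**

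Inputs from section 5.5: Aβ42 baseline mean 294 and SD 54 ng/L, within-person correlation 0.98, a fall of about 5%, two-sided 5% two-sample t-test, 40 prazosin and 20 placebo.

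- SD of change = 54 × √(2 × (1 − 0.98)) = 54 × 0.2 = 10.8 ng/L, as printed.
- Difference = 0.05 × 294 = 14.7 ng/L.
- Standard error = 10.8 × √(1/40 + 1/20) = 2.96. Noncentrality = 14.7 / 2.96 = 4.97 on 58 degrees of freedom, giving power of 99.8%.

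The plan states 90%, which its inputs do not reproduce. With 40:20 and 14.7 ng/L, 90% corresponds to an SD of change of about 16.3 ng/L. That mismatch is a separate matter; both SDs are used here to give a range.

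Let f be the share of the prazosin arm measured off drug and L the fraction of effect lost. The expected difference is 14.7 × (1 − f × L). The documents give neither f nor L, so these values are assumptions.

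| f | L | Difference, ng/L | As % of 294 | Power, SD 10.8 | Power, SD 16.3 |
|---|---|---|---|---|---|
| 10% | 1 | 13.23 | 4.5 | 99.3% | 83% |
| 20% | 1 | 11.76 | 4.0 | 97.4% | 74% |
| 30% | 1 | 10.29 | 3.5 | 92.8% | 62% |
| 10% | 0.5 | 13.96 | 4.75 | 99.6% | 87% |
| 20% | 0.5 | 13.23 | 4.5 | 99.3% | 83% |
| 30% | 0.5 | 12.50 | 4.25 | 98.6% | 79% |

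These rows hold the SD fixed. Mixing on-drug and off-drug participants also adds variance in the prazosin arm. With that included, a normal approximation at f = 30% and L = 1 gives 90.5% (SD 10.8) and 61% (SD 16.3), so the picture is unchanged.

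**The case against.** A reader might infer that item 4b flatly contradicts the rule on late measures and that these LPs will be off drug. The documents do not go that far.

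- Nothing says that dosing ends when the other trial's treatment period is complete. This study's own end-of-study visits also follow its stable-dose period. Item 4b does not set aside the rule on late measures, so the two can be read together.
- The two-week extension could keep a participant on drug until the LP. Whether the other trial would supply it cannot be seen from these documents.
- If the hoped-for week-4 visit takes place, blood pressure monitoring might fall within treatment, and participants may decline that monitoring (section 5.6). The 7-day lag is therefore not inevitable.
- The rule on late measures is itself garbled. It limits end-of-study measures to two weeks past the baseline LP, which cannot be met in a study with about 10 weeks of treatment.
- Off-drug LPs are not confined to dual enrolment: section 5.6 asks early withdrawals to attend the final visits.
- At the printed SD, even the worst row of the table stays above 90%.

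All of this stands, and it makes the conflict conditional. It does not remove it. The extension is optional, the week-4 match is only attempted, and item 4b is a positive instruction that, followed literally, allows an off-drug primary outcome.

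**Conclusion.** The point holds conditionally. Unless dosing continues until the outcome LP, which no section requires, item 4b conflicts with the bar on end-of-study measures after prazosin has stopped and departs from the main schedule. It concerns phase II only, since dual-enrolled participants enter that phase directly. Outright contradiction, or an established off-drug primary outcome, is not supported.

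The probable direction is dilution of the treatment difference. Its size cannot be fixed. The power ranges rest on an assumed 10% to 30% of the prazosin arm being affected. The lower figures also assume complete loss of effect and an SD of 16.3 ng/L that is back-solved from the stated power and does not appear in the plan. The three-month washout in section 5.3 suggests that the sponsor allows for lingering effects, so complete loss is best read as a worst case. The point merits correction because the remedy is cheap and the affected measurement is the primary outcome.

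**What to change.** 1. Reconcile item 4b, the dual-enrolment paragraph, the Study Treatment Period text and the rule on late measures, including its reference to the baseline LP, so that one statement gives study-drug status at the outcome LP for all participants. Which rule applies is for the sponsor to decide; no dose or clinical rule is proposed here.
2. Record the date and time of the last study-drug dose at the final LP.
3. In section 5.5, prespecify a sensitivity analysis, applied identically to both arms, that excludes LPs taken after study drug had ended. It should cover dual-enrolled participants and early withdrawals, and report how many LPs are affected in each arm. Because it excludes participants on a post-randomization event, it should accompany the primary analysis and not replace it.

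The cost is a revision of wording, one case report form field, one additional analysis, and some visit coordination with the other trial, which the protocol already intends.

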#### **Detailed Descriptions of Study Assessments:**

• Structured Clinical Interview for DSM-5 Axis I Disorders (SCID5): A widely used structured interview that assesses Axis I psychiatric history. The SCID has very good reliability and validity. The SCID will be used at the screen visit to rule out exclusionary diagnoses and to describe the subject sample.

PTSD/TBI Glymphatic Protocol Version 3	VA Puget Sound IRB Protocol Template Version: 2/2015	Page 32 of 45
Revised 11/02/2018		

b If more than two weeks will have passed between screen LP visit, then platelet count and clotting time labs will be drawn at these visits.

<sup>c If DNA is already available in a research repository, it will not be collected. If an LP has been performed within two weeks of randomization, and sample is available in the repository, LP will not be done at baseline visit 2.

<sup>dFor second and third QCC, an abbreviated follow up version will be used

<sup>e There may be up to three additional titration visits, which would add three weeks to the total length of the study.

f Blood and saliva for DNA will only be collected at first biomarker collection visit.

g At routine titration / follow up visits, an abbreviated, 1 page version of the PSQI will be used.

- Structured Clinical Interview for DSM-IV Axis I Disorders (SCID-IV): Previously version of the same widely used structured interview that assesses Axis I psychiatric history. The SCID has very good reliability and validity. The SCID will be used at the screen visit to rule out exclusionary diagnoses and to describe the subject sample. If clinically or logistically more accessible, due to previous assessments undergone by this particular subject or new information on the relative utility of the different instruments, we may carry out and/or accept the SCID for DSM-IV or the MINI in place of the SCID5. The SCID for DSM-IV has been a widely used structured interview that assesses Axis I psychiatric history according to the DSM-IV criteria, and is still administered in many of the ongoing research studies here at the MIRECC. The Mini International Neuropsychiatric Interview (MINI)(Sheehan et al., 1998) is a widely used alternative that is also designed to take into account the International Classification of Disease (ICD) 10 criteria, and is widely used internationally.
- Clinician-Administered PTSD Scale for DSM-5 (CAPS): A structured clinical interview designed to assess the symptoms of PTSD outlined in the DSM-5. The CAPS allows the interviewer to make current (past month) and lifetime diagnoses of PTSD. The frequency and intensity of each symptom on the CAPS is rated on separate 0-4 scales. The CAPS has become the standard for psychopharmacologic outcome trials in PTSD.
- Combat Experiences Scale (CES): Will be used to describe the degree of combat trauma exposure in the study sample. Scores range from 1-18. The CES has been utilized in many studies evaluating combat Veteran samples and is relevant to any war zone setting from WWII to OEF/OIF/OND.
- Traumatic Life Events Questionnaire (TLEQ) modified: A 23-item self-report measure of 22 types of potentially traumatic events including natural disasters, exposure to warfare, childhood abuse, and community violence, developed and validated by VA researchers. Traditionally this scale was designed around the DSM-IV, and for each event, respondents are asked to provide the number of times it occurred and whether fear, helplessness or horror was present. However, with the criterion for the experience of fear, helplessness or horror having been removed from the definition of PTSD in DSM-5, and with our interest in potential physiologic impacts of traumatic exposures, which may vary based on the age at which an event was experienced and the time since the event, we have modified the TLEQ to replace the questions about the experience of fear/helplessness/horror with the question "At approximately what age(s) did this happen?"
- STOP-Bang Sleep Apnea Screening: A widely used screening tool that uses 8 yes/no questions to screen for individuals having an elevated risk of obstructive sleep apnea (OSA) sufficient to warrant further evaluation. The STOP-Bang will be used to assess for indications of OSA to be used as covariates in later analysis. In addition, those who screen positive for an elevated risk of OSA and who have not been evaluated for OSA will be provided with appropriate referral options for further evaluation, either by referral to the VA sleep medicine service (for Veterans) or by referral to community providers (non-Veterans and requesting Veterans).
- Montreal Cognitive Assessment (MoCA): A clinician-administered instrument designed to detect mild cognitive impairment, providing a brief assessment of short-term memory recall, executive function, sustained attention, calculation, language, and orientation. Scores range from 0-30, with lower scores indicating greater cognitive impairment. Test-retest reliability is high, with less than one point variation. Internal consistency is good (Cronbach alpha=0.83). To correct for education, 1 point is added for those with less than 12 years of education.

- Patient Health Questionnaire-9 (PHQ-9): The 9-item depression module of the Patient Health Questionnaire, a self-report version of the PRIME-MD used to diagnose major mental disorders. The PHQ-9 items correspond with DSM-IV criteria for depression, with each item scored from "not at all" to "nearly every day." Items of the PHQ-9 are internally consistent (alpha = 0.86-0.89) and the questionnaire exhibits high test-retest reliability coefficients. Agreement between the PHQ-9 and clinician-based interview diagnosis of major depression is high, with a sensitivity of 88% and a specificity of 88% using a PHQ-9 score ≥ 10.
- General Anxiety Disorders-7 (GAD-7): A 7-item self-report questionnaire assessing generalized anxiety symptoms that has been broadly assessed for reliability and validity as a measure of anxiety across the general population. Each item assesses the participant's frequency of experiencing a different common anxiety symptom over the past two weeks on a scale of "not at all" / "several days" / "over half the days" and / "nearly every day". Each response can be assigned a number from 0-3, and the responses can be summed to provide a simple quantification of overall anxiety.
- Pittsburgh Sleep Quality Index (PSQI): A self-report questionnaire assessing sleep quality and disturbances over a 1-month time interval. Nineteen individual items generate seven subscale scores: subjective sleep quality, sleep latency, sleep duration, habitual sleep efficiency, sleep disturbances, use of sleeping medication, and daytime dysfunction. A global score may be obtained by summing the seven component subscales (total score range: 0-21).
- Veterans' RAND-12 (VR-12): A shorter version of the Veterans SF-36, which was based on the administration of the Medical Outcomes Study SF-36 to a large sample of Veterans. The Veterans SF-36 differs only slightly from the standard SF-36, in that the physical and social role scales are converted from dichotomized choices to 5-point ordinal response options to reduce floor and ceiling effects. The SF-12V assesses the same 8 heath concepts (physical functioning, role limitations due to physical problems, bodily pain, general health, vitality, social functioning, role limitations due to emotional problems, and mental health) as the SF-36V but uses fewer items for 7 of the 8 scales. Results are expressed as physical and mental component summaries. Scores on the SF-12V have been shown to correlate strongly with the Veterans SF-36. The SF-12V is the "gold standard" for measuring health related quality of life, owing to its established reliability, validity, and widespread adoption in clinical treatment trials.
- Defense and Veterans Pain Rating Scale (DVPRS): A visual pain rating scale assessing the severity of pain in various areas of the body and how much pain affects the participant's daily activities, sleep, mood, and stress.
- PTSD Checklist for DSM-5 (PCL) without Criterion A: A well validated 20-item self-report measure assessing severity of PTSD symptoms consistent with DSM-5 criteria, with scores ranging from 0 to 80.
- Alcohol Use Disorders Identification Test-Consumption (AUDIT-C): A 3-item modification of the AUDIT questionnaire that enquires about frequency and quantity of typical alcohol consumption, and the frequency with which the respondents report an episode of heavy drinking in the past year. The AUDIT-C demonstrates excellent sensitivity and specificity for detection of heavy drinking and is used as a standard screening tool for alcohol problems in VA primary care settings.

- Quantification of Cannabis Consumption (QCC): A brief questionnaire developed by our research group in consultation with local cannabis researchers that enquires about frequency, quantity and methods of typical cannabis consumption. The questionnaire has been designed around local consumption patterns since the state-level legalization of cannabis use in Washington state, assessing the use of edible and concentrated forms of cannabis as well as smoked forms. The questionnaire also includes questions about subjects' experiences with the effects of cannabis on their mental health and daily functioning.
- Caffeine, Sugar and Nicotine (CSN) assessment: A 1 page questionnaire developed by our research group that draws two items from the Fagerstrom test for nicotine dependence and adds a general frequency of use assessment of different sources of nicotine, caffeine and sugar and some of the primary motivations for this use. This assessment is designed to rapidly accomplish two things: first, to assess for levels of caffeine and nicotine use that are likely to be directly affecting sleep structure or quality, and second, to detect any large changes in patterns of use over the course of the study.
- Neurobehavioral Symptom Inventory (NSI): A 22-item questionnaire designed to assess the presence and severity of common cognitive, emotional, sensory, and somatic symptoms that can occur after traumatic brain injury. Patients rate on a 5-point scale the extent to which each symptom has affected them (rated from "absent" to "very severe"). Anchor descriptions are provided for level of severity. This scale is widely used in VAs across the country as part of the standardized TBI Comprehensive Evaluation.
- Wechsler Test of Adult Reading (WTAR): Will be used to assess premorbid intellectual ability. This measure has excellent internal consistency (0.90 to 0.97), high test-retest reliability (>0.90), and it correlates highly with WAIS-III Verbal IQ (r=.75) and Full Scale IQ (r=0.73). This test typically takes 5 minutes or less to complete.
- Auditory Consonant Trigrams Test (ACT): A measure of short term working memory in which individuals will be asked to recall a series of items after a delay. During the delay, they are asked to complete an interference task (like mental arithmetic). This test takes approximately 5 minutes to complete.
- Symbol Digit Modalities Test (SDMT): Will be used to measure processing speed and divided attention. The participant is provided with a coding key that contains 9 abstract symbols, each paired with a number. Then the participant is asked to fill in empty boxes with the correct number, using the key described above. In part 1 of the task, the participant writes down the answers. In part 2 of the task, they say the answers out loud. This test takes approximately 5 minutes to complete.
- California Verbal Learning Test-II (CVLT): A measure of verbal learning and memory. It has also been shown to be a reliable measure of learning and memory (with internal consistency values ranging from .78 to .94). This measure takes 15-20 minutes to complete.
- Dot Counting Test: Developed in the 1940s as a test of effort and used with minimal modification since this time, this test consists of 12 cards with differently grouped patterns of dots, which subjects are asked to count as quickly as possible. The test has been assessed for validity in a wide variety of populations including those with MCI or mild AD, depression, brain injuries, stroke, and populations with learning disabilities. This measure typically takes less than 5 minutes to complete.

- Emotional Stroop Test: This test is a widely used measure of the extent to which affective arousal interferes with cognitive processing. It can be tuned to different categories of emotionally arousing stimuli, including combat-related terms, and has been found to be particularly sensitive to the presence of PTSD in combat Veterans, including OEF/OIF Veterans. It is a computerized test where an individual is shown one word at a time and asked to identify the color of the word being shown, and the reaction time as a function of whether the word presented is one with a positive affective tone, a negative affective tone, is neutral, or is combat related, is assessed. It is compatible with simultaneous recording of pupil diameter (pupillometry) to correlate results with an independent physiologic measure of affective arousal, vigilance, and locus ceruleus activity in particular. It takes 15-20 minutes to complete this task.
- Psychomotor Vigilance Test (PVT): This test is a widely used measure of behavioral alertness, with high sensitivity to both acute and chronic sleep deprivation, as well as sensitivity to restoration of healthy sleep. It is a computerized test that is given in 5-minute or 10-minute versions, where subjects are asked to press a button each time a visual stimulus appears on the computer screen. The stimulus appears at random inter-stimulus intervals, and both response time and false starts are recorded. The 10-minute PVT has been shown to be highly reliable across a wide variety of populations, and has no measurable learning effects with repeat administration. It is compatible with simultaneous recording of pupil diameter (pupillometry) to correlate results with an independent physiologic measure of affective arousal, vigilance, and locus ceruleus activity in particular.
- Pupillometry: Pupil diameter provides a noninvasive real-time physiologic measure of affective arousal, vigilance and locus ceruleus activity. Pupil diameter will be recorded using an eyetracking-based pupillometry system both at rest and during the performance of the computer-based neurocognitive tests (the PVT and the Emotional Stroop). This equipment monitors pupil diameter using a camera placed at a distance from the participant's eye and carries no additional risk to the participant.
- Actigraphy: The Actiwatch Spectrum Plus (Philips Respironics, Bend, OR) is a wristwatchlike device that measures gross motor activity, integrates the degree and intensity of motion. and records an activity count per a specified epoch length. Recorded activity may vary from zero (no activity) to hundreds per epoch (high activity). An activity count for each epoch is downloaded from the device to a computer program (Actiware, Philips Respironics, Bend, OR), and analyzed using standard statistical software. Sleep variables calculated include total sleep time, total time spent in bed, sleep onset latency, number of awakenings, sleep efficiency, and wake time after sleep onset.
- Blood Pressure (BP) monitoring: The SpaceLabs OnTrak ambulatory blood pressure monitoring system consists of a blood pressure cuff connected to a small computerized device that is programmed to inflate the cuff and take and record a BP measurement at preprogrammed intervals. The previous version of this same device has been used by researchers to demonstrate a connection between PTSD and/or trauma exposure, and a failure to display the normal nighttime drop in BP that occurs during sleep.
- Heart Rate (HR) Monitoring: The CamNTech Actiwave cardio ambulatory single channel ECG waveform recorder consists of two electrodes connected by a short lead, which clip onto two standard ECG pads worn on the chest; the entire unit weighs only 10.3g, and can

record up to 31 hours of data at 128Hz resolution. A tri-axial accelerometer is built into the unit as well, to facilitate correlation of the recorded data with sleep and activity states. The recorded data can be used to assess baseline HR during wake and sleep states, as well as HR variability, a measurement frequently used to provide an indication of both sympathetic and parasympathetic activity during both wake and sleep.

• Consensus Sleep Diary-E (CSD-E): A pre-printed form in calendar format used for self-report of quantitative and subjective measures of sleep quality, completed on a daily basis during the same periods that the participant is wearing an actigraph. The CSD-E includes two sections, one to be completed in the morning upon awakening and the other to be completed before bed. This sleep diary is based on consensus recommendations of sleep experts.

